#### 6.2 SUMMARIES OF CONDUCT OF STUDY

The clinical database will be used to assess study conduct. The number of patients who enroll, discontinue, or complete the study will be summarized. Reasons for premature study treatment discontinuation and study discontinuation, any eligibility criteria deviation, and other major protocol deviations will also be tabulated.

### 6.3 SUMMARIES OF DEMOGRAPHIC AND BASELINE CHARACTERISTICS

Demographic and baseline characteristics (e.g., age, sex, race), baseline safety (e.g., baseline vital signs and laboratory test results), and baseline disease characteristics (e.g., baseline GA area, baseline BCVA, annualized prebaseline GA growth rate) will be summarized for all randomized patients by treatment group using descriptive statistics.

#### 6.4 EFFICACY ANALYSES

The primary and secondary efficacy analyses will be based on the modified intent-to-treat population (see DAP for detailed definition). Patients will be grouped according to the treatment assigned at randomization. Patients in the sham control Q4W and sham control Q8W groups will be pooled in the analyses.

If not otherwise specified, analyses of efficacy outcome measures will be stratified by HtrA1 risk-variant carrier status (HtrA1 risk-variant carrier vs. HtrA1 risk-variant non-carrier, as determined by the HtrA1 risk-variant genotyping assay; see Appendix 3), baseline GA lesion size ( $< 9.0 \text{ mm}^2 \text{ vs.} \ge 9.0 \text{ mm}^2$ ), and annualized prebaseline GA progression rate ( $< 1.9 \text{ mm}^2/\text{yr} \text{ vs.} \ge 1.9 \text{ mm}^2/\text{yr}$ ). A data-as-observed approach with the mixed-effect model will be used to handle missing data in the primary analysis. Sensitivity analyses will be performed to evaluate the effect of missing data on the results (see DAP for details).

#### 6.4.1 Primary Efficacy Endpoint

The primary efficacy endpoint is the mean change in GA area from baseline to Week 72 as measured by FAF.

Comparison of each active arm versus the pooled sham-control arm will be assessed using a linear mixed-effect model with an effect for treatment and with covariate adjustments for baseline factors such as HtrA1 risk-variant carrier status, baseline GA lesion size, and annualized prebaseline GA progression rate. The primary analysis will be based on all available data up to 72 weeks, with no imputation for missing data. Two-sided 80% confidence interval will be provided for the estimated treatment effects. Hypothesis testing will be conducted at the two-sided significance level of 20%, and no multiple-testing adjustment is planned.

Detailed specifications of the statistical methods will be described in the DAP.

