### 2.1 EFFICACY OBJECTIVES

## 2.1.1 Primary Efficacy Objective

The primary efficacy objective for this study is to evaluate the efficacy of ITV injections of 20 mg FHTR2163 administered Q4W or Q8W in patients with GA secondary to AMD compared with sham control on the basis of the following endpoint:

 Mean change in the GA area from baseline to Week 72 as measured by fundus autofluorescence (FAF)

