## 2.1.3 Exploratory Efficacy Objectives

The exploratory efficacy objectives for this study are as follows:

- To evaluate the efficacy of ITV injections of 20 mg FHTR2163 administered Q4W or Q8W in patients with GA secondary to AMD compared with sham control on the basis of the following endpoint:
  - Mean rate of change in the GA area, estimated based on GA area as measured by FAF at four timepoints: baseline, Week 24, Week 48, and Week 72
- To evaluate the efficacy of ITV injections of 20 mg FHTR2163 administered Q4W or Q8W in patients with foveal-involving GA and in patients with non-foveal-involving GA compared with sham control on the basis of the following endpoints:
  - Mean change in the GA area from baseline to Week 72 as measured by FAF
  - Mean rate of change in the GA area, estimated based on GA area as measured by FAF at four timepoints: baseline, Week 24, Week 48, and Week 72

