### STUDY DESIGN

### 3.1 DESCRIPTION OF THE STUDY

This is a Phase II, multicenter, randomized, single-masked, sham-controlled study evaluating the safety, tolerability, and efficacy of 20 mg FHTR2163 dose administered Q4W or Q8W by ITV injections for approximately 76 weeks, in patients with GA secondary to AMD. Approximately 360 patients (144 patients in FHTR2163 Q4W arm, 72 patients in FHTR2163 Q8W arm, and 144 patients in pooled sham arm) will be enrolled in the study at approximately 77 investigational sites in the United States. Site investigators will be qualified ophthalmologists.

[figure not shown]
The study will consist of the following:

- Screening period of up to 120 days, divided into a prebaseline screening period (Day –120 to Day –31) and a baseline screening window (Day –30 to Day –1)
- Treatment period of up to 68 weeks (Day 1 to Week 68 for the Q4W treatment arms and Day 1 to Week 64 for the Q8W treatment arms)
- Primary analysis timepoint visit (Week 72)
- Final study visit (Week 76)

The duration of the study is approximately 76 weeks after the last patient is randomized to the study.

Figure 1 presents an overview of the study design. Schedules of activities are provided in Appendix 1 and Appendix 2.

Figure 1 Study Schema

GA = geographic atrophy; N = number; Q4W = every 4 weeks; Q8W = every 8 weeks.

To be eligible for the study, patients must satisfy all eligibility criteria (see Section 4.1) at both the screening visit(s) and the Day 1 visit (i.e., day patient is enrolled and study drug is administered).

One essential eligibility criterion is that patients will be required to have two FAF images, a prebaseline image and a baseline image performed on a Heidelberg platform obtained at a minimum of ~3 months (84 days) and maximum of ~11 months (336 days) prior to the baseline screening visit. The prebaseline and baseline FAF images may be obtained in two different approaches as illustrated in Figure 2 and described below.

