### 3.3 RATIONALE FOR STUDY DESIGN

The primary efficacy objective of this Phase II study is an anatomic endpoint, specifically, the growth rate of GA lesion area based on FAF imaging (Biarnes et al. 2015). The anatomic primary endpoint provides a more sensitive, quantitative, and earlier metric of GA progression and serves as a surrogate for vision loss. The 76-week study length was designed because of the slow progressing nature of the disease and to maximize the opportunity to ascertain a treatment effect (Fleckenstein et al. 2018).

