#### 6.1 DETERMINATION OF SAMPLE SIZE

This study is designed to evaluate the efficacy of FHTR2163 administered ITV Q4W and Q8W to patients with GA secondary to AMD. The focus of the efficacy outcome analyses will be on estimation of the magnitude of the treatment effect.

The primary efficacy endpoint is the mean change in GA area from baseline to Week 72 as measured by FAF. The sample size provides reasonable precision for estimation of the treatment effect with respect to the primary endpoint.

Approximately 360 patients will be randomized in a 2:1:1:1 ratio to one of four treatment groups: FHTR2163 Q4W, sham control Q4W, FHTR2163 Q8W, or sham control Q8W. Patients in the sham control Q4W and sham control Q8W groups will be pooled in the analyses.

Assuming a 15% dropout rate by Week 72 and a standard deviation of 1.82 mm² for change from baseline in GA area at Week 72 (estimated from the lampalizumab Phase II Study CFD4870g and the Phase III Studies GX29176 and GX29185), 114 patients in the FHTR2163 Q4W arm and 114 patients in the pooled sham-control group will provide 80% power to detect a targeted difference of 0.56 mm² (20% reduction relative to sham control) in the change from baseline in GA area at Week 72 between the FHTR2163 Q4W arm and the pooled sham-control arm. Calculations were based on two-sided t-test at the significance level of 20% and resulted in a total sample size of 285. No multiplicity adjustment is planned for this study.

A total of 131 patients had enrolled in this study as of 10 April 2020. As a result of the increase in missed visits, missed dosing, and missed assessments as a consequence of the COVID-19 pandemic, up to approximately 75 patients will be enrolled in addition to the originally planned 285 patients to help mitigate the potential impact on treatment effect and data.

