#### 6.8 BIOMARKER ANALYSES

The primary efficacy analysis described in Section 6.4 will be repeated in the HtrA1 risk-variant carrier and non-carrier subgroups as an exploratory analysis. Biomarkers will be analyzed together with PK data to explore PK/PD relationships. Additional analyses will be performed to identify biomarkers that are predictive of response to FHTR2163, are associated with rate of progression to a more severe disease state, are associated with susceptibility to developing adverse events, can provide evidence of FHTR2163 activity, or can increase the knowledge and understanding of disease biology.

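### Do the growth-rate wording in Section 3.3 and the unnamed visit term in Section 6.4.1 leave the primary quantity open?

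*Combined protocol and SAP*

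**What the plan says.** Section 2.1.1 gives the primary endpoint as "Mean change in the GA area from baseline to Week 72 as measured by fundus autofluorescence (FAF", and the synopsis and Sections 6.1 and 6.4.1 repeat that definition. Section 3.1 names Week 72 as the visit for the primary analysis. Section 2.1.3 places a different quantity among the exploratory endpoints: "Mean rate of change in the GA area, estimated based on GA area as measured by FAF at four timepoints", namely baseline and Weeks 24, 48 and 72.

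Section 3.3, which explains the design, words it differently: "The primary efficacy objective of this Phase II study is an anatomic endpoint, specifically, the growth rate of GA lesion area".

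Section 6.4.1 opens by restating the Week 72 endpoint. It then says that each active arm is compared with pooled sham "using a linear mixed-effect model with an effect for treatment and with covariate adjustments for baseline factors", and adds: "The primary analysis will be based on all available data up to 72 weeks, with no imputation for missing data". It leaves detailed specification to the DAP, as do the opening of Section 6 and Sections 6.4 and 6.4.2.

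**The concern.** The protocol itself treats change at Week 72 and rate of change as separate endpoints, so growth rate in Section 3.3 cannot be dismissed as a pure synonym. Taken literally, the same quantity is primary in Section 3.3 and exploratory in Section 2.1.3.

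The model summary does not settle the matter by itself. FAF is taken at Weeks 24, 48 and 72, and a mixed model on all data to Week 72 could deliver a Week 72 contrast or a slope. Section 6.1 says "The focus of the efficacy outcome analyses will be on estimation of the magnitude of the treatment effect", so the identity of the primary estimate matters here more than in a trial judged mainly on a p-value. The choice also carries forward, because Section 6.8 says "The primary efficacy analysis described in Section 6.4 will be repeated in the HtrA1 risk-variant carrier and non-carrier subgroups". The two quantities agree in general only if the treatment difference grows in proportion to time.

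**Working it through.** **1. Which quantity does the sample size use?** Inputs from Section 6.1: difference 0.56 mm² and SD 1.82 mm², both for change at Week 72; two-sided α = 0.20; power 80%; dropout 15%; allocation 2:1:1:1 with the sham groups pooled.

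- n per group = 2(z₀.₉₀ + z₀.₈₀)² × (SD/difference)² = 2 × (1.2816 + 0.8416)² × (1.82/0.56)² = 2 × 4.508 × 10.5625 = 95.2, so 96 evaluable.
- With dropout: 96/0.85 = 112.9, so 113, against 114 stated.
- Power with 114 × 0.85 = 96.9 per group: SE = 1.82 × √(2/96.9) = 0.2615; 0.56/0.2615 − 1.2816 = 0.860, which gives 80.5%.
- Total: 114 + 3 × 57 = 285, as stated.

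The design figures reproduce, and their inputs are all Week 72 inputs. No growth-rate SD or growth-rate target appears.

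**2. How far apart could the two quantities be?** The least-squares slope over Weeks 0, 24, 48 and 72, scaled to 72 weeks, weights the four visits by −0.9, −0.3, 0.3 and 0.9. Hold the true Week 72 difference at 0.56 mm² and let the effect follow the shapes below, as fractions of 0.56. The shapes are assumptions.

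| Effect shape | Fractions at Weeks 0, 24, 48, 72 | Slope ratio | Slope × 72 weeks (mm²) |
|---|---|---|---|
| Linear | 0, 1/3, 2/3, 1 | −0.1 + 0.2 + 0.9 = 1.00 | 0.560 |
| Starts at Week 24 | 0, 0, 0.5, 1 | 0.15 + 0.9 = 1.05 | 0.588 |
| Full by Week 48 | 0, 0.5, 1, 1 | −0.15 + 0.3 + 0.9 = 1.05 | 0.588 |
| Full from Week 24 | 0, 1, 1, 1 | −0.3 + 0.3 + 0.9 = 0.90 | 0.504 |

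On a yearly scale the linear case is 0.56/72 × 52 = 0.404 mm² per year.

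**3. With dropout.** Assume 144 per arm, 5% lost before each FAF visit, random intercept variance 25, a random slope, and measurement error making up 10–30% of the Week 72 variance. A generalised least-squares slope, scaled to 72 weeks, then gives 0.536 to 0.608 mm² over the non-linear shapes (−4% to +9%). The Week 72 contrast from a treatment-by-visit model gives 0.560 in every case.

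**4. Power for the Q4W comparison at the enlarged size.** 144 × 0.85 = 122.4 per arm. SE for Week 72 change = 1.82 × √(2/122.4) = 0.2326, and 0.56/0.2326 − 1.2816 = 1.126, so power is 87.0%. If measurement error is a share s of the Week 72 variance, the scaled slope has variance 1.82² × (1 − 0.1s), which is nearly the same. Its power runs from 81.2% (ratio 0.90, s = 0) to 90.1% (ratio 1.05, s = 30%).

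**5. What the protocol expects.** Section 3.3.5.3 says that lesion growth in the intended population is roughly linear. If that holds within each arm, the between-arm difference is linear too, and the first row of the table applies: the two quantities coincide.

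**The case for a change.** The best case for acting is that Section 3.3 is current text, that no DAP wording can make that sentence agree with Section 2.1.1, and that the correction would cost almost nothing. It can be pressed further. Read as a complete specification, a model with one treatment effect and no time term would estimate an average over visits. With a linear effect that is 0.56 × 48/72 = 0.37 mm², clearly not the Week 72 difference. And linear natural growth does not guarantee a linear drug effect, since onset could be delayed.

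The wording point stands: Section 3.3 is loosely phrased. It names no visits, estimator or analysis, however, and nobody choosing the primary estimate would prefer it to the objectives, the sample-size section and the analysis section, which all agree.

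The point about the model does not stand as a defect. Section 6.4.1 fixes the endpoint as Week 72 change before it describes the model, and it presents the description as a summary to be completed in the DAP. Visit terms, the interaction and the covariance structure are normal content for that document. Nothing in the protocol says that a visit-averaged effect will be fitted. The possibility of a delayed effect is real, but it bears on which quantity is the better choice, and the protocol has already chosen.

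**Conclusion.** No change to the plan follows. The Section 3.3 wording is a clerical slip in a rationale paragraph. The unnamed visit term and Week 72 contrast are details that the analysts would fill in sensibly from the stated endpoint. The intended primary quantity is clear: mean change in GA area from baseline to Week 72, each active arm against pooled sham. The sample size rests on it and reproduces to within one patient per group.

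Even if someone did report the growth rate instead, the difference would be nil under linear effects. Under the assumed non-linear shapes it would be −10% to +5% with complete data, or −4% to +9% with the assumed dropout. Those ranges rest on effect shapes, dropout timing and measurement-error shares that the documents do not give. The conclusion also assumes that the DAP, which was not supplied, carries the Week 72 endpoint through to a Week 72 contrast. Nothing in the supplied text suggests otherwise.

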Randomization will be stratified by HtrA1 risk-variant carrier status (HtrA1 risk-variant carrier vs. HtrA1 risk-variant non-carrier), baseline GA lesion size (<9.0 mm² vs. ≥9.0 mm²), and annualized prebaseline GA progression rate (<1.9 mm²/yr vs. ≥1.9 mm²/yr). HtrA1 risk-variant carriers and HtrA1 risk-variant non-carriers may be enrolled in either FHTR2163 or sham-control arms.

After randomization on Day 1, patients will be administered the first ITV injection of FHTR2163 or sham control by the investigator. If a site has an unexpected issue (e.g., unable to assign the study kit), with the Medical Monitor's permission, the patient's first study treatment may be administered within 3 working days of the Day 1 visit. The following assessments will be repeated on the day of the study treatment: slit lamp examination, indirect ophthalmoscopy, and pre- and post-treatment intraocular pressure (IOP) measurement (and recorded on the Day 1 electronic Case Report Form [eCRF]).

Subsequent study treatment visits will be scheduled Q4W or Q8W relative to the Day 1 visit date. Study treatment should not occur earlier than 22 days after the previous treatment. Missed study treatments will not be made up.

At the subsequent visits, patients will have safety evaluations performed by the investigator prior to receiving study drug or sham control. Patient self-administered anti-microbials pre- and post-injection may be used at the investigator's discretion. Patients will be educated as to signs and symptoms of post-injection adverse events and instructed to contact the investigator at any time if they have any health-related concerns. All assessments for a scheduled visit will be performed on the same day, (with the exception of assessments performed during the prebaseline screening period or baseline screening window, which may be performed at any time during the 90-day or 30-day time frame, respectively). After the Day 1 visit, if a patient misses a study visit when ocular images are scheduled to be taken (see Appendix 1 and Appendix 2), the images must be obtained at the next scheduled visit.

Patients who are prematurely discontinued from study treatment (but have not withdrawn consent) will be encouraged to undergo as many scheduled visits as possible with emphasis on completing Week 72 visit.

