Patients discontinued from the study prior to completion will be asked to return for an early termination visit after a minimum of 30 days have elapsed following the final study treatment for monitoring of adverse events and the early termination visit assessments. Early termination visits not completed after 6 months following the last treatment will be considered as "loss of follow-up" when appropriate.

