# 5.1.1 Potential Risks Associated with FHTR2163

#### 5.1.1.1 Potential Ocular Risks

# **Ocular Inflammation**

In repeat-dose GLP toxicology studies of up to 6 months in duration in cynomolgus monkeys, an anterior and posterior intraocular inflammatory response was observed in animals treated with FHTR2163. The observed inflammation was consistent with a generalized non-specific immune response to a heterologous protein, rather than direct

effects of FHTR2163, because of the character and localization of the inflammation and because the incidence and/or severity of inflammation generally lacked a relationship to dose. The inflammation noted during optical coherence tomography, ophthalmic examinations, or microscopic examinations also showed complete or partial recovery.

In the FHTR2163 Phase I clinical study (GR39821), there was one patient with 2 nonserious Grade 1 iritis events. Both events resolved with topical treatment and the patient completed the study with no changes in study drug administration.

In the ongoing Phase II clinical study GR40973, there have been reports of inflammation of the anterior chamber only, posterior chamber only, as well as combined anterior and posterior chamber. These include two serious cases of vitritis and one of serious case of uveitis; and nonserious recurrent vitritis events that lead to study discontinuation. The mechanism is not fully understood at this point.

As of 26 March 2021, there have been no reports of IOI in the ongoing Phase II study GR42558.

Refer to the FHTR2163 Investigator's Brochure for more details on ocular inflammation events in the completed and ongoing clinical studies.

The safety plan includes BCVA, detailed ocular examinations, including slit lamp examinations and indirect ophthalmoscopy, as well as SD-OCT imaging at most study visits to evaluate any potential ocular adverse event. A follow-up call 14  $(\pm 5)$  days after all study drug administrations is required to query for adverse events; particularly any signs or symptoms of decreased visual acuity and/or inflammation (e.g., painful red eye, floaters, scotoma, pain); if the patient reports any concerning signs and/or symptoms, the patient must be evaluated by the investigator as soon as possible.

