#### 6.9 OPTIONAL INTERIM ANALYSES

Given the hypothesis-generating nature of this study, the Sponsor may choose to conduct up to two interim analyses. The decision to conduct an optional interim analysis and the timing of the analysis will be documented in the Sponsor's trial master file prior to the conduct of the interim analysis. The interim analysis will be performed by the unmasked IMC and will be interpreted by the IMC and appropriate senior management personnel. Access to treatment assignment information will follow the Sponsor's standard procedures. The details of the timing and scope of the interim analysis, if any, will be specified in the IMC Agreement.

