- s Recommend the slit lamp examination be performed prior to dilating eyes; for grading scales for anterior and vitreous cells, see Appendix 6.
- t Aqueous humor sample must be collected from the study eye after pretreatment IOP measurement, but prior to study drug administration, when applicable. For a detailed description of the anterior chamber paracentesis and aqueous humor sample collection procedures, see Appendix 14 and the laboratory manual.
- u FAF, keratometry, SD-OCT, OCT-A (as applicable), NI images, and color fundus photographs will be obtained from both eyes and will be forwarded to the central reading center. Note: After randomization, if a patient misses a study visit where ocular images were scheduled to be obtained, the images should be obtained at the next scheduled visit.
- v Only one keratometry measurement on each eye (obtained at prebaseline screening or baseline screening) is required.
- w OCT-A is mandatory for sites that have the capability.
- \* All assessments (including a detailed examination to evaluate for signs of intraocular inflammation) and sample collection should be completed prior to study drug administration except for post-treatment finger-counting and IOP measurement.
- After study drug administration in the study eye only, a finger-counting test followed by hand motion and light perception tests (when necessary) will be performed by the investigator within 15 minutes post study drug injection followed by an IOP measurement that will be obtained between 30–50 minutes post-injection. If there are no safety concerns, the patient may be discharged from the clinic. If the IOP is increased ≥ 10 mmHg from pre-injection measurement, the IOP will measured again at 60–80 minutes post-injection. If the IOP value remains a concern to the investigator, the patient will remain in the clinic and will be treated in accordance with the investigator's clinical judgment prior to discharge. For guidance on adverse event reporting, see Section 5.3.5.2.

- z Record any concomitant medications (e.g., prescription drugs, over-the-counter preparations other than protocol-specified procedural medications [e.g., dilating drops or fluorescein dyes] and pre- and post-injection medications [e.g., proparacaine]) used by the patient from 7 days prior to Day 1 to until the study completion/discontinuation visit.

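### Does the Week 72 primary analysis need a stated rule for autofluorescence images taken off schedule?

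*Combined protocol and SAP*

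**What the plan says.** Section 6.4.1 defines the primary endpoint as the change in GA area from baseline to Week 72 on FAF, analysed with a linear mixed-effect model. On data it says "The primary analysis will be based on all available data up to 72 weeks, with no imputation for missing data". Section 6.4 adds that data are used as observed. Sections 6, 6.4 and 6.4.1 leave the detailed specification to the DAP.

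Two procedures produce FAF images outside the scheduled Weeks 24, 48 and 72.

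- **Make-ups.** Section 3.1 says that after a missed visit "the images must be obtained at the next scheduled visit". Footnote u of Appendices 1 and 2 says "the images should be obtained at the next scheduled visit". After Week 72 the next visit is Week 76 in every arm, where FAF is not otherwise scheduled.
- **Early termination.** Appendices 1 and 2 mark FAF at this visit. Section 3.1 asks patients who leave the study to attend an "early termination visit after a minimum of 30 days have elapsed following the final study treatment", with an outer limit: "Early termination visits not completed after 6 months following the last treatment will be considered" lost to follow-up when appropriate.

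Section 6.1 plans for the loss: "Assuming a 15% dropout rate by Week 72".

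**The concern.** The 72-week bound in Section 6.4.1 can be read as a nominal visit or as a calendar day. It cannot be a strict day cut-off: Week 72 is day 504 after Day 1 and its window runs to day 509. Read literally, it leaves out the Week 76 make-ups that sites are told to obtain. It admits termination images taken before Week 72, without saying at which timepoint they count. The model summary does not mention visit terms, a covariance structure or a Week 72 contrast.

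GA grows steadily, so an image labelled with a later visit than its true date understates growth. If more patients leave the active arms, such labelling favours the drug. Section 5.1.1.1 reports "nonserious recurrent vitritis events that lead to study discontinuation", which makes unequal dropout conceivable, and Section 6.9 says "the Sponsor may choose to conduct up to two interim analyses". A labelling rule chosen after an unmasked efficacy look would be open to question.

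Two wording differences add to the impression of looseness: the verbs in the make-up rule, and Section 3.3, which describes the primary measure as a growth rate although Section 2.1.3 lists the rate as exploratory.

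**Working it through.** **1. The plan's own figure.** Inputs from Section 6.1: difference 0.56 mm², SD 1.82 mm², two-sided 20% level, 80% power, 15% dropout.

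n = 2 × (1.2816 + 0.8416)² × 1.82² / 0.56² = 95.2, so 96 evaluable per arm. 96 / 0.85 = 112.9, so 113, against 114 stated. With 114 × 0.85 = 96.9 evaluable, power is 80.4%. 114 + 114 + 57 = 285. The figure reproduces.

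**2. Growth per week.** The target is a 20% reduction, so sham change is 0.56 / 0.20 = 2.80 mm² and active change is 2.24 mm². Section 3.3.5.3 describes growth as approximately linear: 2.80 / 72 = 0.0389 mm² per week on sham and 2.24 / 72 = 0.0311 on active.

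**3. Week 76 make-ups.** With ±5-day windows, Week 72 covers days 499–509 and Week 76 days 527–537, a gap of 18 to 28 days. Four weeks of growth is 0.156 mm² (sham) or 0.124 mm² (active) per affected eye. The rates of missed images below are assumptions.

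- *Counted as Week 72, no drug effect, 10-point imbalance:* 0.156 × 0.10 = 0.016 mm².
- *Counted as Week 72, design effect, 5% to 15% in both arms:* 0.56 + f × (0.156 − 0.124) = 0.562 to 0.565 mm².
- *Design effect, 5% sham and 15% active:* 0.56 + 0.05 × 0.156 − 0.15 × 0.124 = 0.549 mm². With the rates reversed, 0.577 mm².
- *Left out, earlier images ignored:* at 144 per arm, 144 × (0.85 − m) evaluable. Power is 86.9% for m = 0, then 85.3%, 83.6% and 81.6% for m = 5%, 10% and 15%.
- *Left out, mixed model using earlier images:* if 2% to 10% of completers miss Week 72, the variance of the contrast rises by 0.1% to 1.7%.

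Either reading is harmless at the current sample size.

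**4. Week 24 and 48 make-ups.** The next visit is 4 weeks later in Q4W arms and 8 weeks later in Q8W arms. Pooled sham is half of each, so 6 weeks on average. If 10% are missed everywhere and labelled with the missed visit, the gap between pooled sham and Q4W active is 0.10 × (6 − 4) × 0.0389 = 0.008 mm² at that earlier visit. It is the same size with opposite sign for Q8W active. It reaches the Week 72 estimate only through the model.

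**5. Early-termination images.** At most 0.15 × 360 = 54 patients. The table gives the simulated shift of the Week 72 contrast relative to leaving these images out. Settings: no drug effect, 150,000 per arm, linear growth, dropout uniform in time and unrelated to growth, measurement SD 0.2–0.4 mm², unstructured visit model. All shifts favour the drug.

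| Label given to the image | 17.5% active, 12.5% sham | 20% active, 10% sham |
|---|---|---|
| Nearest visit | 0.009–0.013 mm² | 0.017–0.021 mm² |
| Next visit | 0.030–0.036 mm² | 0.057–0.068 mm² |

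Nearest-visit labelling is 0.009 / 0.56 = 1.6% to 0.021 / 0.56 = 3.8% of the target. With a standard error of about 0.22, the chance of a false benefit is P(Z > 1.2816 − shift / 0.22), which rises from 10% to between 10.7% and 11.8%. Next-visit labelling with the larger imbalance takes it to about 17%.

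With equal dropout and no drug effect there is no bias. With equal 15% dropout and the 0.56 mm² effect, the estimate shrinks by 0.005–0.007 mm² (nearest, about 1%) or 0.017–0.020 mm² (next, 3% to 4%).

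**The case for a change.** The strongest case for acting is that nothing supplied forbids the worst label. If every early-termination image counted as Week 72, dropout of 20% on active and 10% on sham would create about 0.13 mm² of apparent benefit with no drug effect, 23% of the target. Equal dropout is not neutral either if the drug works, as the attenuation above shows. The trial tests at a two-sided 20% level without multiplicity adjustment, missed assessments are the stated reason for enlarging it, and stating windows costs only wording.

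Part of this stands: the supplied text is incomplete, and anyone holding the DAP would look there for image windows and the Week 72 contrast before an unmasked efficacy analysis. The rest is weaker.

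- Labelling every termination image as Week 72, or as the next visit, carries an observation forward. That sits badly with data used as observed and no imputation.
- Section 5.1.1.1 gives neither arm nor rate for the discontinuations, so the 5- and 10-point imbalances are assumptions.
- Sections 3.1 and 4.6.1 ask patients who stop treatment to keep attending, and Section 3.1 stresses Week 72. Termination images therefore come only from those who leave the study and then return when asked.
- Section 4.2.2 keeps the reading centre masked, and Sponsor staff other than committee members masked until database lock. Interim analyses are optional.

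**Conclusion.** No change to the plan follows. This is detail the protocol assigns to the DAP, and the text it does give points competent analysts to a sound answer: observed data, no imputation, a Week 72 endpoint, and either ordinary visit windows or image dates. Under those choices make-up images move the contrast by less than 0.02 mm² or cost at most 1.7% of variance, and early-termination images move it by about 0.01–0.02 mm² with a 5- to 10-point dropout imbalance and no drug effect. Requiring Week 76 images to be included, or termination images to be left out, would depart from the literal wording of Section 6.4.1 for little gain.

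The two verbs in the make-up rule send the image to the same visit. The growth-rate phrase in Section 3.3 is rationale text, overridden by the endpoint definition in Sections 2.1.1, 6.1 and 6.4.1. Both are clerical.

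The sizes rest on near-linear growth, dropout unrelated to growth rate, and assumed rates of missed images and dropout. The conclusion would weaken if the DAP adopted a carry-forward label and the arms lost patients very unequally; nothing in the documents indicates either.
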